1. STUDY SUMMARY

Study rationale: Premature infants are a highly transfused group, though robust evidence supporting neonatal transfusion practice is scarce. The PlaNeT-2/MATISSE platelet transfusion trial found that a 25×10^9 /L platelet count threshold was superior to a 50×10^9 /L threshold in preterm infants, with higher mortality and major bleeding rates in the latter liberal threshold group. (1) There are no neonatal transfusion guidelines that have been implemented by Europe as a whole, resulting in significant variation in transfusion practice within Europe. Detailed contemporary data on neonatal transfusion practices in Europe, including the use of platelet transfusions, are lacking.

Study population: preterm infants born below 32 weeks gestation admitted to a tertiary level Neonatal Intensive Care Unit (NICU)

Study design: prospective, international, multicenter, observational study

Study data collection: data collection took place from September 2022 to August 2023. All participating centers collected data during a fixed six-week study period. Local sites documented transfusion use in all infants in their NICU during these weeks, including infants already admitted at the start of the study period or newly admitted during the study period. Consequently, not all infants were followed from birth, and the duration of study follow-up varied, with a maximum follow-up of 42 days per included patient.

 ${\it Infographic was made using images of Juicy_Fish from FlatIcon}.$

2. STUDY OUCOME MEASURES

We aim to publish separate papers describing neonatal RBC, platelet and plasma transfusions. Therefore, this SAP only focuses on the use of platelet transfusions.

2.1 Main study outcome measures

- 1. Platelet transfusion day prevalence rate
- 2. Case-mix adjusted platelet transfusion day rate
- 3. Cumulative incidence of receiving at least one platelet transfusion during first 28 days of life

2.2 Other study outcome measures

- 4. Primary indications for platelet transfusion
- 5. Volume, duration and infusion rate of platelet transfusion
- 6. Platelet count prior to platelet transfusion
- 7. Platelet transfusion increment, stratified for transfusion volume
- 8. Transfusion related adverse effects

3. DATA CLEANING

3.1 Data cleaning during study follow-up

The site specific patient data was checked and cleaned after the completion of the study period in that participating center. This data quality check was used to detect outliers and impossible combinations of data entry (e.g. non-chronological dates, transfusions after end of study follow-up , etc.). Additionally, we checked for missing data in the baseline characteristics and outcome data. In case of missing data or ambiguities, the local investigator was contacted and incorrect values were directly corrected in the data management system Castor.

3.2 Data cleaning after completion study follow-up

A final data quality check will be performed once all the centers completed the study period using the same data quality check code. Possible ambiguities that were overlooked during the center specific check will be corrected, where any modifications made will be recorded in the data cleaning code.

4. DATA ANALYSES

4.1 General remarks

All statistical analyses will be performed using R statistical software (Version 4.1.17, R Core Team, 2021) or STATA statistical Software (Version 16.1, Texas, USA). Continuous data will be presented as mean (standard deviation (SD)) or as median (interquartile range (IQR)), where appropriate.

4.2 Missing data

Missing values were limited in the eCRF since the majority of the collected variables were marked as mandatory to fill in. Therefore, we expect very few missing values in the dataset.

We decided in advance how to handle missing data for the following variables:

Variables	Commentary			
Platelet count prior to transfusion	Only recorded if platelet count was available in the 24 hours before transfusion. If left blank, the value is recorded as 'not available'.			
Platelet count after transfusion	Only recorded if platelet count was available in the 24 hours after transfusion. If left blank, the value is recorded as 'not available'.			
Congenital anomalies	If not recorded, we assume that congenital anomalies were unlikely and the value is recorded as '0'.			
Bleeding disorders	If not recorded, we assume bleeding disorders were not present and the value is recorded as '0'.			
Major bleeding	If not recorded we assume no major bleeding occurred and the value is recorded as '0'.			
NEC	If not recorded, we assume no NEC occurred and the value is recorded as '0'.			
Sepsis	If recorded as unknown, we assume no sepsis occurred and the value is recorded as '0'.			
Mechanical ventilation	If recorded as unknown, we assume no mechanical ventilation occurred and the value is recorded as '0'.			
Surgical procedures	If recorded as unknown, we assume no surgical procedures occurred and the value is recorded as '0'.			

For all other variables, the total number of missing values will be reported, with the number of infants who had one or more missing values for the variable.

4.3 Data transformations

For the clinical events, investigators only collected the start date of clinical events (except mechanical ventilation) so no information is available on the duration of the event or the

time to clinical remission. Therefore, we made assumptions about the duration of clinical events, which allows us to use these variables for the case-mix adjusted prevalence rates.

The variables for clinical events were defined as followed:

Clinical events	Definitions				
Major bleeding	The duration of a major bleeding episode is defined as 7 days from day of detection of the major bleeding. For each individual admission one of the values will be assigned: - 0: No major bleeding - 1: Current bleeding episode - 2. Status post bleeding				
NEC	The duration of a NEC episode is defined as 7 days from the day of the first symptoms. For each individual admission day, one of the values will be assigned: - 0: No NEC - 1: Current NEC episode - 2. Status post NEC				
Sepsis	The duration of a sepsis episode is defined as 7 days from the day of the positive blood culture. For each individual admission day, one of the values will be assigned: - 0: No sepsis - 1: Current sepsis episode - 2: Status post sepsis				
Mechanical ventilation	The duration of a mechanical ventilation episode is defined as the period from the postnatal day of start mechanical ventilation until the postnatal day of stop mechanical ventilation. For each individual admission day, one of the values will be assigned: - 0: No mechanical ventilation - 1: Current mechanical ventilation episode - 2: Status post mechanical ventilation				
Surgical procedures	The duration of a surgical procedure episode is defined as 7 days from the day of the surgical procedure. For each individual admission day, one of the values will be assigned: - 0: No surgical procedure - 1: Current surgy episode - 2: Status post surgery				

For these assigned values, it is not possible for infants to go back to a status with a lower value, example given from "1" to "0".

Example. Patient A was followed in the study from postnatal day 1 (equal to day of birth) to postnatal day 28, during which the patient developed a culture proven sepsis episode on day 4. In the study database, the patient was represented by 28 rows each representing one admission day in study follow-up. For this sepsis episode, day 4 and the following six days until day 10 were recorded as "1". Prior to sepsis, day 1 to 3 were recorded as "0" (no sepsis), day 11 to 28 as "2" (status post sepsis).

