5.2 Case-mix adjusted platelet transfusion day prevalence rates

As variation between countries in platelet prevalence rates could be explained by differences in population characteristics and disease severity, we will calculate case-mix adjusted platelet transfusion day prevalence rates adjusted for several patient demographics and clinical variables to allow fair comparison between prevalence rates.

Case-mix adjusted platelet transfusion day prevalence rates will be calculated as followed:

- 1. A logistic regression model is fitted on all data, with case-mix variables and clinical variables as (possible time varying) predictors and platelet transfusion as response variable.
- 2. The model is used to estimate the expected platelet transfusion day prevalence rate per country
- 3. Observed / expected prevalence rate ratio per country are calculated
- 4. Rate ratio are multiplied with overall unadjusted platelet prevalence rate

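### As worded, the no-return rule in SAP section 4.3 codes a later recurrence or reintubation as past while it is current, which can bias the case-mix adjusted country rates

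*SAP*

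**What the plan says.** SAP section 4.3 introduces the coding with "The variables for clinical events were defined as followed" and covers major bleeding, NEC, sepsis, mechanical ventilation and surgical procedures. Each infant has one status per event: none (0), current (1) or past (2).

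- For four events the current period is a fixed week. For sepsis: "The duration of a sepsis episode is defined as 7 days from the day of the positive blood culture". Bleeding, NEC and surgery are handled in the same way.
- Ventilation has recorded limits. The episode runs "from the postnatal day of start mechanical ventilation until the postnatal day of stop mechanical ventilation", and the codes are "1: Current mechanical ventilation episode - 2: Status post mechanical ventilation".
- After the table, one sentence applies to all these values: "it is not possible for infants to go back to a status with a lower value". A move from 1 to 0 is given as an example.

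The worked example that follows (Patient A) has a single sepsis episode. The SAP makes no exception for a second episode or a reintubation.

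Section 5.2.1 enters the five statuses as predictors in the GEE logistic model for a transfusion day. The model's predictions form the expected rate per country (5.2.1), the observed/expected ratio and funnel plot (5.2.2) and the case-mix adjusted rate (5.2.3), which is main outcome 2 in section 2.1. Section 5.2 gives the purpose of the adjustment as "to allow fair comparison between prevalence rates".

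**The concern.** Barring a return from 1 to 0 is sensible, because an infant who has had sepsis is never again an infant without a history of it. The sentence goes further. A move from 2 to 1 is also a return to a lower value, and the 1-to-0 case is offered as an illustration, not as a limit. A programmer who follows the text would take a running maximum, and an infant who reaches 2 would stay there.

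For ventilation two statements then collide. The definition makes a reintubated infant current between the recorded start and stop days, while the no-return rule makes the same days past. Durations had to be assumed for the other four events, but ventilation has a recorded stop day, so that reason does not apply to it.

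At stake is the meaning of the status-post coefficient. It would average recovered days with acutely ill days. A country with more recurrence would then have an expected rate that is too low and a ratio that is too high, and would look more liberal than its practice is. A country with less recurrence would look more restrictive.

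**Working it through.** **1. Reproduce the SAP's own example.** Inputs from section 4.3: culture on day 4, window of the start day plus six, follow-up days 1 to 28, status never falling. Result: days 1–3 = 0, days 4–10 = 1, days 11–28 = 2. This matches the SAP exactly.

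**2. Add a second episode (assumed dates).** The table compares the rule as written with a rule that allows 2 to 1.

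| Episodes | Rule as written | 2 to 1 allowed | Days that change |
|---|---|---|---|
| Sepsis days 4 and 18 | 11–28 = 2 | 11–17 = 2, 18–24 = 1, 25–28 = 2 | 7 |
| Sepsis days 4 and 12 | 11–28 = 2 | 11 = 2, 12–18 = 1, 19–28 = 2 | 7 |
| Sepsis days 4 and 11 | 4–17 = 1, 18–28 = 2 | the same | 0 |
| Sepsis days 4 and 8 | 4–14 = 1, 15–28 = 2 | the same | 0 |
| Ventilation 1–5 and 15–24 | 6–28 = 2 | 6–14 = 2, 15–24 = 1, 25–28 = 2 | 10 |

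The day-8 and day-11 rows assume that a new event extends the running window, which the SAP does not state. If it did not, the day-8 event (days 8–14) would be coded current on days 8–10 and past on days 11–14, so 4 of its 7 days would be miscoded.

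**3. Effect on predicted risk (assumed risks; the documents give none).** Take 4 transfusion days per 100 ventilated days and 0.5 per 100 recovered days. If 10% of the days coded 2 are really ventilated:

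- risk on days coded 2 = 0.10 × 4 + 0.90 × 0.5 = 0.85 per 100
- under-prediction on reventilated days = 4 / 0.85 = 4.7-fold
- over-prediction on recovered days = 0.85 / 0.5 = 1.7-fold

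**4. Effect on the country ratio (assumed).** Two countries of equal size have identical practice, and ventilation status is the only predictor, entered as a three-level category. In each country 50% of days are never-ventilated (0.3 per 100), 15% are first ventilation (4 per 100) and 35% are coded 2. Of all days, a share s is reventilation coded 2.

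O(s) = 0.50 × 0.3 + 0.15 × 4 + 4s + 0.5 × (0.35 − s) = 0.75 + 4s + 0.5 × (0.35 − s)

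E is the same for both countries: the mean of the two O values.

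| s, country A / B | O, A / B | E | O/E, A / B |
|---|---|---|---|
| equal | equal | equal to O | 1.00 / 1.00 |
| 3% / 5% | 1.030 / 1.100 | 1.065 | 0.97 / 1.03 |
| 2% / 6% | 0.995 / 1.135 | 1.065 | 0.93 / 1.07 |
| 2% / 10% | 0.995 / 1.275 | 1.135 | 0.88 / 1.12 |

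**5. Second set of assumptions.** Daily risks are 0.5%, 10% and 1% for true status 0, 1 and 2. Each country has 7000, 1000 and 2000 days coded 0, 1 and 2, and a share r of the days coded 2 is really current.

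O(r) = 35 + 100 + 2000 × [0.10r + 0.01(1 − r)]

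- r = 5% and 15%: O = 164 and 182, E = 173, O/E = 0.95 and 1.05
- r = 5% and 30%: O = 164 and 209, E = 186.5, O/E = 0.88 and 1.12
- r = 10% in both: O/E = 1.00 and 1.00

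Section 5.2.3 multiplies O/E by one overall rate, so the same percentage error passes to the adjusted country rate.

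**The case against.** The authors may have meant only that an infant never becomes event-free again. The one transition they name fits that intent, and their single-episode example does not test anything else. This is a fair reading of what was intended, but it does not change what the sentence says, and the wording would still need correcting.

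The rule also matters only if repeat episodes were recorded. The SAP does not say that the eCRF held several start dates per event or several ventilation periods. Counting infants with at least one episode (section 4.4) is ordinary descriptive wording and does not settle it. This stands: the size of the problem depends on a fact that the SAP does not give.

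Three stronger readings are tempting and are not supported.

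- A reader might infer that every second event is miscoded. An event that starts before status 2 is reached is coded current for some or all of its days.
- A reader might infer that the model loses these days. They stay in it under the status-post coefficient, alongside gestational age, birth weight, postnatal day and the other four statuses. A reintubated infant with a first sepsis is still current for sepsis. The illustrations have a single predictor and so allow no such offset.
- A reader might infer that the country comparison is defeated. With equal recurrence there is no country bias, and the larger figures need wide contrasts: 2% against 6% of all days is 5.7% against 17.1% of the days coded 2, a threefold difference.

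The reach is limited too. The unadjusted prevalence rate (5.1), the cumulative incidence (5.3) and the section 6 outcomes do not use these statuses.

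**Conclusion.** The sentence is wrong as written. Followed literally, it miscodes any episode that begins after status 2 is reached, and for ventilation it contradicts the definition in the same section. The consequence is confined to the case-mix adjusted rate and the observed/expected ratios behind it. Its direction is predictable: countries with more recurrence appear to transfuse more than their practice explains.

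Its size cannot be computed from the documents. Under the assumed risks and shares above, unequal recurrence shifts the country ratio by about 3% to 12% each way, and equal recurrence shifts it by nothing. These figures assume that repeat episodes were recorded and that no other covariate takes up part of the effect. The point should be fixed, but the documents do not show that the between-country comparison is invalid without the fix.

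**What to change.** Replace the no-return sentence in section 4.3 with:

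> Status cannot return to 0 after a first episode; a new episode sets the status to 1 for its duration (7 days, or ventilation start to stop), after which it returns to 2; a new event within a current window extends that window.

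Add a second, recurrent episode to the Patient A example so that the coding can be checked. State as a limitation any event for which only the first episode was recorded, since no recode can recover later ones.

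The cost is small: one sentence, an extended example and a recode from dates already held, with no new data collection. It should be done before the model in section 5.2.1 is fitted.

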4.4 Patient and center characteristics

The following descriptive data on patient and center characteristics will be presented.

Patient characteristics (for total and per country)

- Number of patient included
- Total number of admission days in study follow-up
- Duration of study follow-up per patient, in days
- Postnatal age at start follow-up in the study, in days
- Sex, % female
- Gestational age at birth, in days
- Birth weight, in grams
- Multifetal pregnancy, % singleton
- Patients with congenital anomalies, %
- Patients with intrauterine growth restriction, %
- Patients with at least one major bleeding during study follow-up, %
- Patients with at least one NEC episode during study follow-up, %
- Patients with at least one sepsis episode during study follow-up, %
- Patients with at least one day of mechanical ventilation during study follow-up, %
- Patients with at least one surgical procedure during study follow-up, %

Participating centers (for total and per country)

- Number of academic centers, %
- Number of centers that perform NEC surgery, %
- Number of larger centers (caring >100 preterm infants with a GA below 32 weeks yearly on average), %

5. ANALYSIS OF STUDY OUTCOME MEASURES DESCRIBING PLATELET USE

5.1 Platelet transfusion day prevalence rates

The prevalence rate is the rate of events (new and recurring events) over a specified time period. The platelet transfusion day prevalence rate in a certain time period is defined as the number of platelet transfusion days per 100 NICU admission days in this period. A platelet transfusion day is defined as any day after birth on which the infant received at least one platelet transfusion.

$$\textit{Prevalence rate} = \frac{\textit{Number of RBC transfusions days during study period}}{\textit{Number of admission days in follow up during study period}} \times 100 \ \textit{days}$$

The platelet transfusion day prevalence rate is calculated in each center and pooled per country. We expect a large between country variability, therefore all prevalence rates are pooled using random effects Poisson models described by Stijnen et al. (2010). This model uses the exact within-study likelihood instead of the approximate normal within-study likelihood which is known to perform better with low event rates and small sample sizes. Additionally, this method does not require the use of an continuity correction in case centers have a prevalence rate of 0 platelet transfusion days. (2) Pooling is done using the function "metarate" of the R-package Meta.

Subgroup rates and overall rate will be presented with 95% confidence intervals in a forest plot. Prevalence rates will only presented on country level.

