5.2.1. Average expected platelet transfusion day prevalence rate per country

A logistic regression model is used to estimate the probability that a NICU admission day is a platelet transfusion day based on several covariables, for each individual admission day in study follow-up. To account for the repeated measures within an infant, the model is fitted using generalized estimation equations (GEE).

Probabilities are calculated individually for each patient for each NICU admission day in study follow-up and summarized per country to calculate the average predicted platelet transfusion day prevalence rate.

Average expected RBC transfusion day prevalence rate per country =

Sum of predicted probability per admission day over admission days over infants per country

Number of admission days per country

The following variables are included in the regression analyses. The clinical variables could vary over time and are included under the assumption that experiencing these events leads to an increased risk of transfusion and not vice versa.

- Baseline variables: sex, gestational age at birth, birth weight, congenital anomalies, intrauterine growth restriction (birth weight below 10th percentile) (3)
- Clinical variables: major bleeding, NEC, sepsis, mechanical ventilation, surgical procedure, postnatal day

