5.2.2. Observed / expected prevalence rate ratio per country

The prevalence rate ratio per country is defined as the country's observed platelet transfusion day prevalence (as calculated in section 5.1) compared to the country's average expected platelet transfusion day prevalence rate.

Prevalence rate ratio per country =

Observed platelet day prevalence rate per country

Average expected platelet day prevalence rate per country

Observed / expected prevalence rate ratios will be presented in an observed/expected funnel plot.

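### Section 5.1 intervals treat repeat transfusion days in one infant as independent; they are too narrow for countries with few centres unless the between-centre variance is shared across countries

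*SAP*

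**What the plan says.** Section 5.1 defines the first main outcome as "the number of platelet transfusion days per 100 NICU admission days in this period". It counts repeats: "The prevalence rate is the rate of events (new and recurring events) over a specified time period". With up to 42 days of follow-up per infant (section 1), one infant can contribute several transfusion days.

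Aggregation is by centre: "The platelet transfusion day prevalence rate is calculated in each center and pooled per country". On the model, the section states that "all prevalence rates are pooled using random effects Poisson models", and it adds: "This model uses the exact within-study likelihood instead of the approximate normal within-study likelihood". It chooses the exact likelihood partly because some centres may have no transfusion days. Pooling uses the R function `metarate`, which takes one event count and one person-time per centre. The 95% intervals for countries and overall go into a forest plot. The section names no infant-level term, dispersion parameter or robust variance, and it does not say whether the between-centre variance is estimated within each country or shared.

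Section 5.2.1 models the same outcome by infant-day and does allow for the clustering: "To account for the repeated measures within an infant, the model is fitted using generalized estimation equations (GEE". That model yields the expected rate per country and does not feed back into the section 5.1 intervals. Section 5.2.2 adds: "Observed / expected prevalence rate ratios will be presented in an observed/expected funnel plot". It does not say how the limits are built. Sections 5.2.2 and 5.2.3 name no interval for the ratios or the adjusted rates.

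**The concern.** Within a centre, a Poisson likelihood forces the variance of the count to equal its mean. That fits if transfusion days occur independently. It does not fit if they concentrate in a few infants who are transfused repeatedly. The plan's own case-mix model points to such concentration: its predictors include major bleeding, NEC, sepsis and surgery, each set to last 7 days.

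The centre random effect can pick up the extra dispersion as apparent between-centre variance, but only where there are enough centres to estimate it. If it is estimated country by country, a one-centre country has nothing to estimate it from, and a country with two or three centres has very little.

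Rates are shown at country level only, so the country interval is what a reader will use to judge whether countries differ. If it is too narrow, a chance cluster of a few heavily transfused infants can look like a difference in practice.

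**Working it through.** The SAP gives no rate, number of centres, number of infants or interval width, so there is no figure to reproduce. All sizes below rest on stated assumptions.

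**1. Variance of a centre total.** Assume that transfused infants arrive as a Poisson process and that each has a geometric number of transfusion days X with mean m (X = 1, 2, ...). Then E[X²] = 2m² − m, and the variance-to-mean ratio of the centre total is D = E[X²]/E[X] = 2m − 1. A correct interval is √D times as wide as the Poisson one. A nominal 95% Poisson interval covers about 2Φ(1.96/√D) − 1.

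| m (assumed) | D | √D | Approximate coverage |
|---|---|---|---|
| 1 | 1 | 1.00 | 95% |
| 1.5 | 2 | 1.41 | 83% |
| 2 | 3 | 1.73 | 74% |
| 3 | 5 | 2.24 | 62% |
| 4 | 7 | 2.65 | 54% |

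**2. One-centre country, exact Poisson interval, simulated.** Assumptions: 60 infants, 10% transfused, geometric repeats, 20,000 runs. Coverage is 97% at m = 1, then about 86%, 78%, 68% and 57% at m = 1.5, 2, 3 and 4. These are a little above the approximation. One reason is that the number of transfused infants is binomial here, so D falls to 2m − 1 − 0.1m, which is 2.8 rather than 3 at m = 2.

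**3. Several centres, variance estimated within the country.** Assumptions: 1.5 transfusion days per 100 admission days, about 750 admission days per centre, no true centre differences, random-intercept Poisson model fitted by maximum likelihood with Wald intervals (plain Poisson log-rate interval for one centre).

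| m | 1 centre | 2 | 3 | 5 | 10 |
|---|---|---|---|---|---|
| 1 | 96% | 96% | 96% | 96% | 95% |
| 1.5 | 86% | 86% | 88% | 89% | 92% |
| 2 | 78% | 80% | 83% | 85% | 89% |
| 3 | 69% | 67% | 73% | 79% | 81% |

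With no repeat days (m = 1) there is no loss, so in this setting the repeats cause it. At m = 2 the between-centre variance was estimated as about zero in 60% of runs with two centres, 41% with three and 7% with ten.

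**4. Many centres.** With 10 to 20 centres, the ratio of model standard error to true standard deviation is 0.92 to 0.96 for m = 1.5 to 2, and 0.79 to 0.86 for m = 3. The width shortfall is therefore small to moderate.

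**5. Variance shared across countries.** With 60 equal centres and the variance estimated over all of them, coverage in a one-centre country is about 95% (m = 1.5), 95% (m = 2) and 91% (m = 3).

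**6. Candidate remedy.** In the setting of step 2, a log-scale interval with infant-clustered variance covers about 91% to 94%. A percentile bootstrap of infants covers about 87% to 90%.

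**The case against.** The strongest reply is that the planned model may already deal with the problem. Section 5.1 speaks of random-effects models with subgroup rates and does not say that the variance is fitted country by country. If it is shared, step 5 shows that even a one-centre country is covered at or near the nominal level. This stands, and it makes the conclusion conditional.

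It is also fair that the size is unknown. Repeat days per infant and centres per country are not in the document, and with no repeats the problem vanishes. Nor does all under-coverage with few centres come from repeat days. With true centre variation (standard deviation 0.3 on the log scale) and no repeats, the planned interval covers 85% with one centre and 89% with five.

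A reader might infer three further things that the text does not support:

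- **The overall rate ignores the country level.** Section 5.1 does not describe the structure of the overall model. The sentence "We expect a large between country variability" is given there as the reason for using random effects.
- **The funnel plot will flag too many countries.** Section 5.2.2 does not say how the limits are set, so this would follow only if plain Poisson limits were used.
- **The forest plot will show false differences.** The plan describes rates with intervals and states no between-country test or outlier rule.

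What remains is that section 5.1 names nothing at infant level for an outcome whose within-infant correlation section 5.2.1 accepts, and that it leaves open the one choice that decides whether this matters.

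**Conclusion.** The point holds in conditional form. The section 5.1 likelihood treats repeat transfusion days in one infant as independent. If the between-centre variance is estimated separately per country, the 95% intervals of countries with one or few centres are too narrow, with one-centre coverage of about 86% to 57% for an assumed mean of 1.5 to 4 transfusion days per transfused infant.

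It would be wrong to read this as equal narrowing everywhere. With 10 or more centres, and for the overall rate, the loss of width is small to moderate, and a shared variance removes most of the problem. The point estimates are not in question. The percentages rest on geometric repeats and on the assumed rates and centre sizes, none of which the SAP gives. The change should be made because the country interval is the main product of this outcome and the remedy is cheap.

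**What to change.** Keep the planned point estimates and state in section 5.1 how the between-centre variance is estimated. Then take one of two routes for the country rates:

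1. Give log-scale 95% intervals with an infant-clustered (robust) variance. The database already holds one row per infant-day (example in section 4.3), so no new data are needed.
2. Share the between-centre variance across countries, so that it carries the extra dispersion.

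Where a country has no transfusion days, keep the exact Poisson limit, because a log-scale interval cannot be formed.

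Use the same infant-clustered variance for the observed/expected ratios in section 5.2.2, and allow for over-dispersion in the funnel limits.

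Two other remedies fit less well. A Poisson model with infant random effects estimates a rate conditional on the infant effect, which does not match the retained point estimate. A percentile bootstrap of infants still under-covers (step 6) and collapses to a zero-width interval when there are no transfusion days.

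The cost is a few lines of SAP text, modest extra analysis and wider intervals for small countries. Route 1 still falls slightly short of 95% in a small single centre, and this should be said when the results are reported.
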